APPENDIX II: Procedure for Applying for a Certificate of Confidentiality

1 LIST OF ABBREVIATIONS

Abbreviation	Definition
ACDS	Adult ADHD Clinical Diagnostic Scale
ADD	Attention Deficit Disorder
ADHD	Attention Deficit Hyperactivity Disorder
AE	Adverse Event
AISRS	Adult ADHD Investigator Symptom Rating Scale
ALP	Alkaline Phosphatase
ALT/SGPT	Alanine Aminotransferase/Serum Glutamic Pyruvic Transaminase
ASI-Lite	Addiction Severity Index-Lite
AST/SGOT	Aspartate Aminotransferase/Serum Glutamic Oxaloacetic Transaminase
BDNF	Brain-derived neurotrophic factor
BE	Benzoylecgonine
BSCS	Brief Substance Craving Scale
BUN	Blood Urea Nitrogen
CAP	College of American Pathologists
CBT	Cognitive Behavioral Therapy
CGI-O	Clinical Global Impression Scale – Observer
CGI-S	Clinical Global Impression Scale – Self
CLIA	Clinical Laboratory Improvement Amendment of 1988
COMT	Catechol-O-methyltransferase
СРК	Creatinine phosphokinase
CYP2D6	Cytochrome P450 2D6
Del	Deletion
dL	Deciliter
DSM-IV	Diagnostic and Statistical Manual of Mental Disorders Fourth Edition
DTR&D	Division of Treatment Research and Development
ECG	Electrocardiogram
eCRF	Electronic Case Report Form
EST	Expressed sequence tags
GABRG2	Gamma-aminobutyric acid receptor gamma 2 subunit gene
GGT	Gamma glutamyltranspeptidase
HAM-D	Hamilton – Depression Rating Scale
HIV	Human immunodeficiency virus
HRBS	HIV Risk-Taking Behavior Scale
HWE	Hardy-Weinberg Equilibrium
Ins	Insertion
kg	Kilogram
LAAM	Levomethadyl acetate (L-alpha acetylmethadol)
LDH	Lactate dehydrogenase
LD	Linkage disequilibrium
mg	Milligrams
mL	Milliliter
MAO	Monoamine oxidase

Abbreviation	Definition		
MCV	Mean corpuscular volume		
MCH	Mean corpuscular hemoglobin		
MCHC	Mean corpuscular hemoglobin concentration		
MINI	Mini International Neuropsychiatric Interview DSM-IV version		
NIDA	National Institute on Drug Abuse		
NTS	Nicotine transdermal system		
OTC	Over-the-counter		
ROS	Reactive oxygenation species		
RPR	Rapid plasma reagin (test for syphilis)		
SAE	Serious adverse event		
SNPs	Single nucleotide polymorphisms		
SR	Sustained-release		
SSRI	Selective serotonin reuptake inhibitor		
SUR	Substance use report		
Vss/F	Volume of distribution		
VMAT-2	Vesicular monoamine transporter-2		

2 STUDY SCHEMA

3 PROTOCOL SYNOPSIS

STUDY OBJECTIVES: The primary objective of this study is to assess the efficacy of bupropion in reducing methamphetamine use in subjects with methamphetamine dependence who report using methamphetamine 29 or less days during the 30 days prior to signing consent. It is hypothesized that bupropion, compared to placebo, will be associated with an increase in the proportion of subjects who achieve abstinence (confirmed by at least two methamphetaminenegative urines and no methamphetamine-positive urines) each week during the last two weeks (Weeks 11 and 12) for non-daily users. Secondary objectives include but are not limited to: assessing the success or failure to achieve abstinence (confirmed by at least two methamphetamine-negative urines and no methamphetamine-positive urines) each week during the last two weeks (Weeks 11 and 12) for subjects using methamphetamine 18 or less days during the 30 days prior to signing consent, assessing the safety of bupropion in this study population, assessing other measures of efficacy of bupropion in reducing methamphetamine use or craving, and other psychological assessments of methamphetamine dependence. In addition, if efficacy findings are promising, preliminary evaluations of the genetic markers associated with a positive clinical outcome or predictive of bupropion safety and efficacy including associations with bupropion pharmacokinetics (PK) may be performed.

STUDY DESIGN: This is a double-blind, placebo-controlled, parallel-group design study in which, after an up to 4-week screening period which includes a 2-week baseline assessment period, 200 subjects will be randomly assigned in an approximately 1:1 ratio to either receive placebo or bupropion (100 subjects per group) daily for 12 weeks, with follow-up assessments weekly for 4 weeks after completion of study interventions. Adaptive randomization will be used to balance study intervention groups within each clinical site, based on methamphetamine use (18 or less days *versus* 19-29 days out of 30 days prior to signing consent), severity of depression symptoms [Hamilton Depression Rating Scale (HAM-D) score ≤ 12 *versus* >12], and presence of adult Attention Deficit/Hyperactivity Disorder (Adult ADHD Clinical Diagnostic Scale - ACDS).

STUDY POPULATION: Two hundred treatment-seeking individuals with Diagnostic and Statistical Manual of Mental Disorders Fourth Edition (DSM-IV) criteria for methamphetamine dependence determined by Mini International Neuropsychiatric Interview (MINI) DSM-IV version will be randomized to receive either bupropion or placebo. Only those subjects who report 29 or less days of methamphetamine use in the 30 days prior to signing consent will be considered for enrollment. Males and females, 18 to 65 years-of-age, inclusive, with at least one methamphetamine-positive urine specimen provided during the screening or baseline period prior to randomization (or provide collateral information to verify recent use if a positive urine sample can not be obtained), who verbalize the ability to understand and provide written informed consent, will be included.

INTERVENTIONS: Subjects randomized to the bupropion group will receive 150 mg of sustained-release (SR) bupropion once daily for 3 days then twice daily, i.e., a total of 300 mg/day, for a total of 12 weeks (dose taper will be performed the last 3 days of the 12 weeks, to 150 mg per day). Subjects randomized to the placebo group will receive matched placebo tablets according to the same schedule. All subjects will receive two 60 minute early recovery group

sessions after signing consent but before randomization, and manual-guided group cognitive behavioral therapy (CBT) consisting of three 90 minute sessions/week during the 12 weeks of study interventions and once weekly during the 4 weeks of follow-up.

SAFETY ASSESSMENTS: All subjects enrolled in the study will have a physical examination, a 12-lead electrocardiogram (ECG), and clinical laboratory studies (blood chemistry, hematology, Hepatitis B and C virus serology, syphilis test, tuberculin test, and urinalysis) performed during screening. If the potential participant is female, a pregnancy test will also be performed during screening, on the first day of investigational product administration, at Study Weeks 4, 8, and 12 or earlier termination. Vital signs, concomitant medication use, and a urine screen for other substances of abuse will be assessed weekly during the study. Adverse events (AEs) will be assessed at each visit. At the end of the study, or if terminated early, subjects will be evaluated for AEs, vital signs, physical examination, clinical laboratory studies, and ECG.

EFFICACY ASSESSMENTS: The primary efficacy outcome measure is a binary measurement of treatment success or failure, where a subject who successfully achieves two weeks of abstinence during the last two weeks of investigational product dosing (Weeks 11 and 12) is scored as a success. A successful outcome requires that (1) all urine samples tested in the last two weeks are negative for methamphetamine (< 300 ng/mL quantitative result of negative qualitative result) and (2) a minimum of two urines samples are collected and tested per week during Weeks 11 and 12. The study population for the primary efficacy outcome measure includes non-daily users defined as subjects with methamphetamine dependence who reported using methamphetamine 29 or less days during the 30 days prior to signing consent. A subject who drops out before the last 2 weeks of the intervention phase is scored as a failure in the analysis. A subject who stays on study to the beginning of Week 11 but who does not provide at least 2 urine samples per week during Weeks 11 and 12 is scored as a failure. Secondary assessments include analyses of other measures of success in the reduction of methamphetamine use, including but not limited to success or failure to achieve abstinence (confirmed by at least two methamphetamine-negative urines and no methamphetamine-positive urines) each week during the last two weeks (Weeks 11 and 12) for subjects using 18 or less days during the 30 days prior to signing consent, the log_{10} weekly mean quantitative urine methamphetamine level, the maximum number of days of methamphetamine negative urines, the proportion of successful subjects with different patterns in the reduction in methamphetamine use, the weekly mean proportion and the maximum number of consecutive non-use days by self report, and proportion of subjects who achieve abstinence who remain abstinent through the end of follow-up (Week 16). Additional measures of bupropion effect will include study retention, Addiction Severity Index (ASI)-Lite scores, HAM-D scores, Adult ADHD Investigator Symptom Rating Scale (AISRS) scores, Brief Substance Craving Scale (BSCS) scores, Clinical Global Impression scores as assessed by the subject (CGI-S) and an observer (CGI-O), and the HIV Risk-Taking Behavior Scale (HRBS) score. ASI-Lite and the HRBS are performed during baseline and at study termination. The HAM-D is performed weekly during screening/baseline, every other week during the intervention period, and also once at study termination. The BSCS, CGI-S, and CGI-O are assessed weekly during screening, baseline, and intervention periods, and at study termination. AISRS is measured at baseline, and Weeks 4, 8, and 12, or early termination. Investigational product compliance will be monitored by counting returned investigational product tablets and by measuring bupropion and its major metabolite in urine samples. Effects on other substances of abuse (nicotine, alcohol, and marijuana) will be determined by self-report collected at each visit.

GENETICS EVALUATION: For subjects who consent to the genetics part of the study, blood will be collected before the start of investigational product administration for analysis of genetic variants and if the subject is randomized into the study, during Study Weeks 6 and 12 for analysis of gene expression profiles during interventions to evaluate genetic variants and genes associated with positive clinical outcomes and safety. The Affymetric 500K Array set will be used to identify susceptibility genes for methamphetamine dependence, with the special emphasize on those genes involved in the dopaminergic reward system as well as gene expression profiles of subjects in response to bupropion over different time points. Conduct of these analyses will be dependent upon favorable efficacy findings.

Blood will be collected before investigational product administration and during Study Weeks 6 and 12 for bupropion levels and plasma brain derived neurotrophic factor (BDNF) levels, to examine associations between genetic variants expression levels, bupropion pharmacokinetics (PK), plasma BDNF levels, and clinical response. Elevated plasma BDNF levels are associated with methamphetamine neurotoxicity, and are known to decline during abstinence from methamphetamine. Since bupropion also has an independent effect on BDNF, plasma samples will be tested for bupropion at the same timepoints as plasma for BDNF is obtained. This will allow the evaluation of whether BDNF is affected differently in subjects receiving bupropion compared to those receiving placebo, and whether this effect influences methamphetamine use or abstinence. In addition, it is also hypothesized that methamphetamine users who have the BDNF 66Val homozygote will be more likely to benefit from bupropion than those who do not.

ANALYSIS: Each of the primary and secondary outcome variables will be analyzed using appropriate statistical methods for the intention-to-treat (ITT) population and for the evaluable population. The ITT population includes subjects who are randomized and receive at least 1 dose of investigational product. The evaluable population is those subjects who meet the eligibility criteria, receive at least 4 weeks of investigational product, and provide at least 2 urine samples per week that were analyzed for methamphetamine during the last two weeks of investigational product dosing period (Weeks 11 and 12). The proportions of subjects who achieve abstinence during Weeks 11 and 12 will be compared between groups using either the Chi-square test or Fisher exact test, as appropriate based on the estimated expectation of the contingency table's cell sizes computed from the table's row and column totals. The effect, if any, of age, race, usual route of methamphetamine use (oral/nasal inhalation versus intravenous/smoked), or clinical site on the primary intervention effect will be determined. Interactions of intervention group with methamphetamine use (18 or less days versus 19-29 days out of 30 days prior to signing consent), severity of depression (HAM-D score ≤ 12 versus >12), and presence of adult ADHD will also be assessed. Statistical tests will be two-sided at a 5% Type I error rate. Ninety-five percent confidence intervals will be two-sided. In addition, all of the above-mentioned endpoints will be compared in a medication-compliant subset of the evaluable bupropion group, a medication non-compliant subset of the evaluable bupropion group, and the evaluable placebo group. Medication-compliant subjects are defined as individuals testing positive for bupropion and/or its major metabolite in at least 50% of urine samples (in the aggregate) collected during

study weeks 1-10 and in at least 66% of urine samples (in the aggregate) collected during weeks 11 and 12.

Summaries of the baseline characteristics of the subject population in both intervention groups will be prepared, for both the ITT and evaluable subject populations. A summary will be prepared to show dropouts/retention over time in each intervention group and for major subgroups. Investigational product compliance of each group will be summarized.

All AEs will be reported in tabular form, indicating the frequency of each type of event by study intervention group, and by the following demographic characteristics such as gender, ethnicity, age, duration of addiction, and all combinations of these characteristics.

Association analysis for either single or multiple single nucleotide polymorphisms (SNPs) (as a block) from GeneChip® Mapping 500K Array will be conducted by using the ALLELLE, CASECONTROL and HAPLOTYPE procedures of SAS/Genetics. CASECONTROL will also be used to compare allele and genotype frequencies in the bupropion and placebo groups using three types of Chi-square tests (i.e., genotype and allele case-control tests and linear trend test) and options for controlling correlation of allele frequencies among members of the same subpopulation. Similarly, we plan to test association using haplotype information from multiple SNPs within a candidate gene/region for the case-control data. In addition, for the bupropion group, we also plan to examine the association between genetic markers and trough plasma levels of bupropion and safety outcomes such as frequency of severity of commonly reported AEs (e.g., insomnia). Furthermore, we plan to analyze interactions between significant genes or SNPs and environmental factors using a generalized multifactor dimensionality reduction method. Conduct of these assays will be dependent upon favorable efficacy findings.

If differentially expressed genes are identified, we plan to use various clustering techniques over different experimental groups to analyze the expression patterns. Expression profiles will be grouped by: a) hierarchical cluster analysis using CLUSTER and TREEVIEW b) quality clustering and c) self-organizing maps. The outputs from each program will be compared with respect to the clusters formed. These data will be used to determine relationships between the clusters, disease status, and intervention group and response.

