15 ANALYTICAL PLAN

15.1 Statistical Hypotheses

Primary Outcome: It is hypothesized that bupropion, as compared to placebo, will increase the proportion of subjects who achieve abstinence (confirmed by at least two methamphetamine-negative urines and no methamphetamine-positive urines) during the last two weeks (Weeks 11 and 12) for non-daily users.

Secondary Outcomes: It is hypothesized that bupropion, compared to placebo, will be associated with an increase in the proportion of subjects who achieve abstinence (confirmed by at least two methamphetamine-negative urines and no methamphetamine-positive urines) each week during the last two weeks (Weeks 11 and 12) for subjects using methamphetamine 18 or less days during the 30 days prior to the start of signing consent. Secondly, it is also hypothesized that bupropion, as compared to placebo, will increase the proportion of subjects with 21 consecutive days of abstinence during which time all urine drug screens must be methamphetamine-negative (both with and without self report), increase the proportion of subjects who reduce their methamphetamine use as compared to baseline use, increase the weekly mean proportion of methamphetamine non-use days according to self-report alone, increase the proportion of methamphetamine negative urine samples, and improve treatment retention. It is hypothesized that bupropion will reduce the severity of methamphetamine dependence, craving, and comorbidity as assessed by the ASI-Lite, the BSCS, the CGI-S, the CGI-O, and the AISRS. It is further hypothesized that in the evaluable population (as defined in section 15.3), bupropion will be significantly more effective than placebo in those subjects who are medication-compliant compared to either the placebo group or subjects who were not medication compliant. This applies to the primary outcome and all secondary outcomes. Medication-compliant subjects are defined as individuals testing positive for bupropion and/or its major metabolite in at least 50% of urine samples (in aggregate) obtained during Weeks 1 through 10 and at least 66% of urine samples (in aggregate) obtained during Weeks 11 and 12.

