15.2.1 Primary Outcome Measure

The primary efficacy outcome measure is a binary measurement of treatment success or failure, where a subject who successfully achieves two weeks of abstinence during the last two weeks of the investigational product dosing period (Weeks 11 and 12) is scored as a success. During the investigational product dosing period, each subject is asked to provide three urine samples per week. A successful outcome requires (1) all urine samples in the last two weeks are negative for methamphetamine (< 300 ng/mL quantitative result of negative qualitative result) and (2) a minimum of two urines samples collected and tested per each of the last two weeks during investigational product dosing. A subject who drops out before the last 2 weeks of the treatment period is scored as a failure in the analysis. A subject who stays on study to the beginning of Week 11 but who does not provide at least 2 urine samples per week during Weeks 11 and 12 is scored as a failure.

15.2.2 Secondary Outcomes Measures Effect on methamphetamine and other drug use during Study Weeks 1-12 (except J)

- A. The secondary efficacy outcome measure is also a binary measurement of treatment success or failure, where a subject who successfully achieves two weeks of abstinence during the last two weeks of the investigational product dosing period (Weeks 11 and 12) is scored as a success. The study population for this outcome measure is defined as those subjects with methamphetamine dependence who report using methamphetamine 18 or less days during the 30 days prior to signing consent.
- B. Methamphetamine non-use weeks during study Weeks 1 through 12. Use weeks are defined as each 7-day period staring with the first day of investigational product administration. A non-use week is any week in which all of the urine drug screens for methamphetamine were negative (< 300 ng/mL). Conversely, a use week is any week in which at least one of the urine drug screens for methamphetamine was positive (≥ 300 ng/mL). If no drug screening results are available, the data for that week is considered as missing.

- **C.** Log₁₀ weekly mean quantitative urine methamphetamine level.
- **D.** The proportion of successful subjects with different patterns in the reduction in drug use examined as follows:

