15.2.3 Additional Secondary Outcome Measures and Analyses

The following additional analyses will be conducted:

i. A novel, non-binary method for evaluating success and failure (McCann and Li, submitted to CNS Neuroscience & Therapeutics) will be used to test the hypothesis that bupropion, as compared to placebo, will increase abstinence from methamphetamine that lasts for multiple weeks and through the end of the 12-week treatment phase. A subject will be regarded as abstinent from methamphetamine during a given week if at least two methamphetamine-negative urines and no methamphetamine-positive urines are provided, and a subject who achieves abstinence during Weeks 11 and 12 will be regarded as a success. A subject who drops out of

the study, provides one or more methamphetamine-positive urines during Weeks 11 and 12, or provides less than two urines per week during Weeks 11 and 12 will be regarded as a failure. For successful subjects, urine results from all weeks prior to Week 11 will be evaluated and, again, they will be regarded as abstinent from methamphetamine during those weeks with at least two methamphetamine-negative urines and no methamphetamine-positive urines. Their degree of success will then be calculated by determining the "Number of Beyond-Threshold Weeks of Success" (NOBWOS), with the threshold set at 1 week of end-of-study abstinence. For example, a subject achieving 8 weeks of end-of-study abstinence (abstinence on weeks 5 through 12) will be assigned a NOBWOS value of 7. Similarly, a subject who achieves the minimum level of success (abstinence on weeks 11 and 12) will be assigned a NOBWOS value of 1. Treatment failures will be assigned a NOBWOS value of 0. NOBWOS values will then be compared between groups using a two-sided Van der Waerden two-sample test.

ii. The relationship between self-reported baseline level of methamphetamine use (number of days reported use during the 30 days immediately prior to screening) and the percentage of urines positive for bupropion and/or its major metabolite throughout the 12-week treatment period for all subjects randomized to the bupropion group will be evaluated using a logistic regression analysis. The percentage of urines testing positive for bupropion and/or its metabolite will serve as the dependent variable and the number of days reported use prior to screening will serve as the independent variable.

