15.4 Analysis Plan

15.4.1 Efficacy Assessments

Each of the primary and secondary efficacy outcome measures listed in sections 15.2.1 and 15.2.2 will be analyzed for the ITT population. The primary outcome measure also will be analyzed and for the "evaluable" and "expanded evaluable" populations. Each of these analyses will be conducted in two ways: 1) comparing the bupropion and placebo groups independent of

compliance data and 2) comparing the medication-compliant subjects in the bupropion group with both the placebo group and the subjects who were not medication-compliant in the bupropion group. Medication-compliant subjects are defined as individuals testing positive for bupropion or its major metabolite in at least 50% of urine samples (in aggregate) obtained during weeks 1 through 10 and at least 66% of urine samples (in aggregate) obtained during weeks 11 and 12. Finally, the analyses described in section 15.2.3 will be conducted for the ITT population.

While there is every intent to be complete in describing the analyses to be performed, it is not possible to anticipate every contingency and some adjustments may be required to meet constraints posed by the structure of the data.

Statistical tests will be two-sided at a 5% Type I error rate. Confidence intervals will be two-sided with a 95% confidence coefficient.

Primary Efficacy Outcome Measure

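### The medication-compliance contrasts sort only the bupropion arm, partly on the Week 11-12 urines that score the primary outcome, so they can favour bupropion when it has no effect

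*Protocol*

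**What the plan says.** The compliance rule stands in the synopsis (Analysis), section 15.1 and section 15.4.1. It has two limbs: "testing positive for bupropion and/or its major metabolite in at least 50% of urine samples" in Weeks 1-10, and positivity "in at least 66% of urine samples (in the aggregate) collected during weeks 11 and 12".

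For the primary outcome, section 15.2.1 says that a subject who "achieves two weeks of abstinence during the last two weeks of the investigational product dosing period (Weeks 11 and 12) is scored as a success", with at least two urines tested in each of those weeks and none positive. Dropouts before Week 11 are failures.

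Section 13.6.29 runs the drug assay on the urine specimens already provided for the methamphetamine assay. That section and the last footnote to Table 1 restrict the assay to the bupropion group.

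The groups compared are "a medication-compliant subset of the evaluable bupropion group, a medication non-compliant subset of the evaluable bupropion group, and the evaluable placebo group" (synopsis). Section 15.4.1 repeats this as "comparing the medication-compliant subjects in the bupropion group with both the placebo group and the subjects who were not medication-compliant in the bupropion group" and applies it to the ITT as well as the evaluable and expanded evaluable analyses. Section 15.1 states it as a hypothesis of superior efficacy in the evaluable population and adds: "This applies to the primary outcome and all secondary outcomes". Tests are two-sided at 5%. Section 15.4.2 labels the adverse-event tests descriptive; no such label is attached here.

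**The concern.** Class and outcome are read from the same specimens, in one arm only. Under section 12.6 a subject may stop tablets and keep all scheduled assessments. A bupropion subject who relapses and stops can therefore remain evaluable, be scored a failure, and leave the compliant group. A placebo subject with the same course stays in the comparator as a failure. In the ITT version, a bupropion subject who has left before Week 11 has no Week 11-12 urines and cannot show 66% positive, while the placebo dropout remains in the denominator.

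At stake is how a null or weak randomized result would be read. A significant compliant-versus-placebo contrast beside it would invite the conclusion that bupropion works in those who take it, when the difference may only show which bupropion subjects were removed.

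**Working it through.** **The plan's own figure.** The protocol gives no figure for the compliance contrasts. Its sample size (section 15.5: success 0.238 against 0.057, 95% power, two-sided 5%, 100 per group) reproduces: exact power of Fisher's test at 100 per group is 0.951. The two rates are used below only to choose a plausible common success rate.

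**Evaluable population, no drug effect.** Let *p* be the true success rate in both arms, and *s* and *f* the probabilities that a success and a failure pass the Week 11-12 limb. If passing the Weeks 1-10 limb is unrelated to outcome, it cancels:

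success among compliant = *p·s* / (*p·s* + (1−*p*)·*f*)

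All of these inputs are assumptions: *p* = 0.25, *s* = 0.9, early limb passed by 80%.

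- No link, *f* = 0.9: 25% in compliant and placebo alike. Simulated two-sided false-positive rate about 4-6%.
- Moderate link, *f* = 0.7: 0.225 / (0.225 + 0.525) = **30%**, against 25% on placebo. Overall compliance is 0.8 × 0.9 = 0.72 for successes and 0.8 × 0.7 = 0.56 for failures, so non-compliant success is 0.25 × 0.28 / (0.25 × 0.28 + 0.75 × 0.44) = 17.5%. False positives: 8-10% against placebo, 18-24% against non-compliant.
- Strong link, *f* = 0.5: 0.225 / (0.225 + 0.375) = 37.5%. False positives: 23-31% against placebo, 57-71% against non-compliant.

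The false-positive ranges cover 60 to 80 evaluable subjects per arm (assumed), with 3,000 simulated trials per setting.

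**Which stops change the class.** With six urines in Weeks 11-12, four must be positive (4/6 = 66.7%). On a Monday, Wednesday, Friday schedule the fourth falls on Monday of Week 12. Sections 4.2.3 and 13.6.29 give a parent peak of 136 ng/mL, hydroxybupropion about 10 times that, a half-life of about 20 hours, and a 5 ng/mL limit. From 1,360 to 5 ng/mL is log2(272) = 8.1 half-lives, about 6.7 days, if urine resembles plasma (an assumption). If urine is ten times lower it is log2(27.2) = 4.8 half-lives, about 4 days. A stop on Friday of Week 11 or later then still passes. Stops by early Week 11 are the ones that mainly matter. For example, a subject positive through Week 8 who then stops and turns negative has 24/30 = 80% positive in Weeks 1-10, passes the first limb, and fails only the second.

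**ITT version, no drug effect.** Let *d* be dropout before Week 11, equal in both arms, and let 70% of completers be compliant regardless of outcome. All successes are completers, so

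success among compliant = 0.7·*p* / (0.7·(1−*d*)) = *p* / (1−*d*)

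With *p* = 0.147, about midway between 0.057 and 0.238:

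| Dropout | Compliant | Placebo | False positives favouring bupropion |
|---|---|---|---|
| 20% | 0.147/0.8 = 18.4% | 14.7% | 7% |
| 30% | 0.147/0.7 = 21.0% | 14.7% | 14% |
| 40% | 0.147/0.6 = 24.5% | 14.7% | 25% |
| 50% | 0.147/0.5 = 29.4% | 14.7% | 42% |

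The last column is from 4,000 simulated trials per row, 100 per arm, two-sided Fisher test, counted in bupropion's favour. With compliance unrelated to outcome it is about 2%. The dropout rates are assumed; as a guide only, section 4.3 cites 42% treatment completion among methamphetamine users.

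**The case against.** The strongest reply has five parts.

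1. **Carry-over.** Metabolite stays detectable for days, so a stop in Week 11 does not automatically change the class. This stands. A reader might infer that any relapse with stopped tablets inside the outcome window turns a subject non-compliant; the protocol's own pharmacokinetics do not support that. It also makes the 50% pass rate for failures look extreme.
2. **No documented link.** A reader might take analyses ii and iii of section 15.2.3 as the protocol's admission that relapse and tablet-taking go together. They relate methamphetamine use before treatment to compliance. They point to baseline confounding, and say nothing on relapse during treatment. This stands.
3. **Assumed pass rates.** None of the pass rates comes from the documents, and with no link there is no bias in the evaluable set. This stands for the evaluable version. It does not answer the ITT version, where dropout alone is enough.
4. **Limited reach.** The hypothesis is listed under secondary outcomes, section 15.2 calls the secondary variables exploratory, and every analysis is also run without regard to compliance. This limits the harm. But section 15.1 still claims superior efficacy, for the primary outcome too, under 5% tests.
5. **Weeks 1-10 is no cure.** It is also measured after randomization, in one arm. If the 90%/70% split applied to Weeks 1-10 instead, the result would be 0.225/0.75 = 30% in compliant against 0.025/0.25 = 10% in non-compliant subjects. This stands, which is why the descriptive label comes first in the fix.

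**Conclusion.** The defect holds, with conditions. The compliance rule shares specimens with the primary outcome and sorts one arm only, so any tendency of failures to miss the Week 11-12 limb more often than successes favours bupropion in both contrasts. In the evaluable population the size is unknown: 30% against 25% under one assumed split, and nothing if there is no link. In the ITT version it needs no relapse-tablet link, only dropout before Week 11: about 18% to 29% against 14.7% at 20% to 50% dropout, assuming equal dropout in the arms and compliance unrelated to outcome among completers.

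A reader might infer that the rule by itself manufactures a drug effect, or that the trial's main result is compromised. The documents support neither. The comparison of randomized arms in the ITT population does not use the compliance class and is unaffected.

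**What to change.** In the synopsis, section 15.1 and section 15.4.1:

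- State that the compliance contrasts are descriptive and are not tests of efficacy.
- For the primary outcome, classify compliance from Weeks 1-10 urines only, so that the class is fixed before the outcome window opens.
- Adjust the contrast with placebo for baseline days of use and baseline urine results.
- Show the present two-limb definition alongside as a sensitivity display.

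The cost is wording in three places. No new data or visits are needed: the baseline data are already collected and the assays go ahead as planned. The change should be made before the assays, which Table 1 places after study closure.

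The downside should be stated in the text. A Weeks 1-10 class is still selection after randomization in one arm and can carry earlier relapse-related stopping. Its 50% threshold is loose: with 30 scheduled urines, 15 positives suffice, so a subject with drug-positive urines for about five weeks and none afterwards counts as compliant. That dilutes the on-drug group, which is the reason to keep the two-limb display.
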